Telemedicine has been introduced in obstetrics for prenatal care, monitoring of chronic conditions during pregnancy, genetic counseling, medical abortion, and colposcopy (Kohn, et al., Griener). A randomized control trial in urogynecology in 2019 demonstrated that telephone-based postoperative visits were non-inferior to in-person postoperative visits in terms of patient satisfaction. (Thompson, et al.) Although utilization of telemedicine in OB/GYN is expanding, there is still a dearth of literature, particularly regarding virtual visits in gynecology. The Cleveland Clinic has instituted telemedicine with the provision of virtual visits in all specialties. In benign gynecologic surgery, virtual visits have been offered in the last couple of years as an alternative to the in-person 2-week post-operative visit, but have not been evaluated systematically.

Our study aims to evaluate the safety and efficacy of virtual postoperative visits as compared to in-office postoperative visits for patients undergoing minimally invasive hysterectomy. We hypothesize that virtual visits will be non-inferior to in-person visits in terms of patient satisfaction. The primary objective for this study is to evaluate patient satisfaction of their postoperative visit experience, as measured by the Press Ganey Medical Practice Survey and Medical Practice Telemedicine Survey (Presson, et al). The secondary objectives include evaluating the incidence of a new diagnosis of a postoperative complication requiring medical treatment (e.g. calling in of a prescription), an office visit with CNP or MIGS surgeon, or an urgent care or ER visit. Post-operative complications include infection (urinary, pulmonary, wound, pelvic abscess, bloodstream), thromboembolic events, bleeding; and issues with wound healing, such as dehiscence. We will record no-show rates, visit times, and estimated travel distance as measured by distance of home to clinic site (Srikrishna, et al).

Study Methods:

This is a two arm, randomized non-inferiority clinical trial.

Setting

This study will take place within the Minimally Invasive Gynecologic Surgery division in the Women's Health Institute of the Cleveland Clinic, Cleveland, OH.

Population

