We will recruit patients undergoing benign minimally invasive hysterectomy (laparoscopic, robotic, and vaginal). Inclusion criteria include patients >18 years of age who are able to provide informed consent without assistance, speak English, and who have access to a phone or device equipped for virtual visits. Patients will be excluded if the staff surgeon determines they are inappropriate for virtual follow-up, if there is suspicion of malignancy, if they are unable to provide consent, or if they do not have access to technology that enables virtual visits.

Inclusion criteria	Exclusion criteria
>18 years of age	Deemed ineligible by staff surgeon
Able to provide consent without assistance	Suspicion of malignancy
English-speaking	Unable to provide consent
Access to phone or device equipped for virtual visits	Do not have access to technology for virtual visits

Recruitment

Enrolled participants will be randomized to either a two-week virtual postoperative visit with a certified nurse practitioner (CNP) or a two-week in-office postoperative visit with a certified nurse practitioner (CNP) in a 1:1 allocation ratio. Block randomizations with block size of 4 will be assigned to nurse providers independently. Randomization schedules will be implemented by Redcap.

Data collection

The primary outcome of this study is patient satisfaction, as measured by the Press Ganey Medical Practice Survey and Medical Practice Telemedicine Survey. These questionnaires will be sent via RedCap on the day of their two-week postoperative appointment. We will provide verbal reminders about study participation and survey administration at the visit. If participants have not responded by their six-week visit, a scripted phone call will be made as a reminder. The secondary outcome is a new diagnosis of a postoperative complication requiring medical treatment (e.g. calling in of a prescription), an office visit with a CNP or MIGS surgeon, or an urgent care or ER visit. Complications include infection (urinary, pulmonary, wound, pelvic abscess, bloodstream); thromboembolic events; bleeding; and issues with wound healing, such as dehiscence. Calvien-Dindo classification system for postoperative complications will be used. We will also look at no-show rates, visit times, and travel distance.

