We will collect basic demographic information from the EMR, including MRN, age, email address, BMI, race, insurance status, parity, and prior surgical history. Date of enrollment, date of surgery, date of admission, and date of discharge will be recorded. Surgical indication, procedure performed, length of hospital stay, and perioperative outcomes (reoperation, readmission, unscheduled office or virtual visits (i.e. earlier than the scheduled 2 week visit), ED/urgent care visits, infection rates) will also be obtained. No-show rates will be obtained through the EMR. We will also note if a planned virtual visit is unable to be completed due to

technical difficulties, or is converted to a telephone visit. We will collect date of their 6 week postoperative visit or date they withdrew from the study. We will collect zip code; travel distance from home to clinic site will be calculated using average travel time with minimal traffic based on participant's zip code using Google Maps.

We will collect the reason for ineligibility for all patients deemed such by staff surgeons.

All participants will be assigned a study number to facilitate de-identification of data.

Data will be compiled in RedCap and securely stored on an encrypted server.

Statistical analysis

Power Calculation:

We hypothesized that patient satisfaction would be non-inferior for patients randomized to the postoperative virtual visit compared to those randomized to in-person virtual visit (Thompson, et al). Sample size of 70 patients in each arm is needed to achieve 90% power to detect a non-inferiority margin of -0.20. Allowing for a dropout rate of 20%, 88 patients will be recruited in each arm.

Analysis plan:

For the primary outcome, the Farrington-Manning score test for non-inferiority will be performed, for both intention-to-treat and per-protocol analyses. Approximately normally-distributed continuous measures will be summarized using means and standard deviations and will be compared using two-sample t-tests. Continuous measures that show departure from normality and ordinal measures will be summarized using medians and quartiles and will be compared using Wilcoxon rank sum tests. Categorical factors will be summarized using frequencies and percentages and will be compared using Pearson's chi-square tests or Fisher's Exact tests.

All analyses will be done using SAS (version 9.4, The SAS Institute, Cary, NC) and a $p < 0.05$ will be considered statistically significant.

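### The secondary complication outcome can be met through an office visit with a CNP, which is also the control arm's allocated visit, so complications that qualify only by that route are scored differently by arm

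*Combined protocol and SAP*

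**What the plan says.** The document's Data collection section describes the secondary outcome in these terms: "a new diagnosis of a postoperative complication requiring medical treatment (e.g. calling in of a prescription), an office visit with a CNP". A visit to a MIGS surgeon serves equally, and attendance at urgent care or an ER is the third route. The objectives at the end of the Background give the same three routes, ending with "an office visit with CNP or MIGS surgeon, or an urgent care or ER visit". The listed complications are infections, thromboembolic events, bleeding and wound-healing problems.

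Under Recruitment, the experimental arm is allocated to "a two-week virtual postoperative visit with a certified nurse practitioner (CNP)" and the control arm to "a two-week in-office postoperative visit with a certified nurse practitioner (CNP)".

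Three further statements in Data collection bear on the point:

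- Severity grading is named: "Calvien-Dindo classification system for postoperative complications will be used". It is not said to decide whether an event counts.
- The visits to be extracted from the record include "unscheduled office or virtual visits (i.e. earlier than the scheduled 2 week visit)". That description stops at the two-week visit.
- Reoperation, readmission, ED/urgent care visits and infection rates are also collected.

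The Analysis plan compares categorical factors by chi-square or Fisher's exact test, with 0.05 as the significance threshold. It has no rule specific to the complication outcome.

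**The concern.** One of the three ways to become an event is a type of contact that the randomisation itself assigns. A control patient is already in the office with a CNP at two weeks; a virtual-arm patient is not. Nothing in the plan says whether the allocated visit satisfies the office-visit route, or whether the visit must be an additional one.

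Safety is part of the stated aim, and this composite is the safety measure named as the secondary outcome. If patients with the same complication are counted or not according to where they were seen, the comparison can show a difference when the true complication rates are equal. That difference could make virtual visits look either less safe or safer.

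**Working it through.** The plan states no rate, margin or power for this outcome, so there is no figure to reproduce. The check sets the definition against the arm descriptions and then illustrates the size.

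**Step 1: score the same complication in each arm, by route.**

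| What the complication needs | Virtual arm | In-office arm |
|---|---|---|
| Medical treatment | event | event |
| Urgent care or ER visit | event | event |
| In-person look only, allocated visit does not count | event if called in | not an event if dealt with at the scheduled visit |
| In-person look only, allocated visit counts | event only if called in | event automatically |

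The first two rows agree across arms. The last two do not, and the sign of the disagreement reverses between them. A wound problem needing inspection but no treatment is the typical case.

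**Step 2: look for text that settles it.** The two statements of the outcome do not exclude the allocated visit. The unscheduled-visit item covers only visits before the two-week visit, so it misses an office visit prompted by the virtual visit. Clavien-Dindo grading is not tied to the event rule.

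**Step 3: illustrate the size.** All rates here are assumptions. Let c be the true complication rate, equal in both arms; f the share of complications that can qualify only through an office visit; and h the share of those in the virtual arm who are called in.

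- Allocated visit does not count, and all such virtual-arm patients are called in: virtual scores c, control scores c(1 − f), difference = +cf.
- Allocated visit counts: control scores c, virtual scores c(1 − f(1 − h)), difference = −cf(1 − h).

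With c = 10% and f = 50%:

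- First reading: 10% − 5% = +5.0 points. This is 0.05 × 88 = 4.4 extra virtual-arm events among 88 recruited, or 0.05 × 70 = 3.5 among 70.
- Second reading: −0.10 × 0.50 × (1 − 0.5) = −2.5 points at h = 0.5, and −0.10 × 0.50 × (1 − 0) = −5.0 points at h = 0.

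Over c = 5% to 20% and f = 25% to 75%, the first reading gives +1.25 points (0.05 × 0.25) to +15 points (0.20 × 0.75). The artefact vanishes if f = 0 or, on the second reading, if h = 1.

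**Step 4: an all-or-none bound.** Suppose 10% of each arm of 88 has a finding that only needs a look: 0.10 × 88 = 8.8, about 9 patients. If all or none of the virtual-arm cases are called in, depending on the reading, the score is 9 v 0 in one direction or the other: 9/88 = 10.2 points. This restates its own assumption and is a worst case for that rate.

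**Step 5: could it reach p < 0.05?** Two-sided Fisher's exact test, 88 per arm:

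| Events | p |
|---|---|
| 5 v 0 | 0.059 |
| 6 v 0 | 0.029 |
| 9 v 0 | 0.003 |
| 9 v 4 (rounding 8.8 v 4.4) | 0.25 |

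If there were no other events, six scored by venue alone would cross the threshold. The 5-point illustration would not.

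**The case against.** The best defence rests on the word requiring. A pre-booked visit that happens regardless is not required by the complication, so the reading on which every control finding qualifies is strained. That is fair, but it leaves the other reading, on which a virtual-arm patient called in is an event and an identical control patient is not.

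A related defence is that the rule could mean a complication needing in-person assessment, judged on need wherever the patient happens to be. That would score the wound example alike in both arms. It is not written in the plan; adopting it would itself change the rule, and the judgement of need could still vary by arm.

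It can also be said that an extra trip to the office is a real consequence of virtual care. It is, and it deserves reporting, but it measures utilisation and not the incidence of complications.

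Two stronger inferences are tempting and should be resisted. A reader might conclude that the trial's whole safety comparison is compromised. The documents do not support that: reoperation, readmission, ED/urgent care visits and infection rates are also collected, though no time window is given for them. A reader might also conclude that every complication is scored differently by arm. Only those qualifying solely through the office visit are; medical treatment, of which a prescription is just one example, and urgent care/ER apply equally to both arms.

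**Conclusion.** The point holds in this limited form. The designated secondary safety outcome contains a qualifying route that overlaps with the control arm's allocated visit, and on either natural reading, complications that depend on that route are scored by arm. This goes beyond missing detail, because following the stated rule can create a difference where none exists.

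The size cannot be derived from the documents. About 5 points at a 10% complication rate with half qualifying only by office visit is an illustration. It assumes, on the first reading, that all such virtual-arm patients are called in or, on the second, that none are. The 9 v 0 result is a bound, not an estimate. The direction depends on a rule that the plan does not state. The satisfaction analysis and the sample size are unaffected.

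**What to change.** 1. Remove the office visit with a CNP or MIGS surgeon as a qualifying condition in both places where the outcome is defined.
2. Make the between-arm comparison the listed complications that require medical treatment or an urgent care/ER visit.
3. As supportive information, tabulate all diagnosed complications by Clavien-Dindo grade and arm, whatever the venue.
4. Record additional office visits in both arms, including those after the two-week visit and excluding the scheduled two-week and six-week visits. Report them by arm as a separate utilisation item.

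The cost is a change of wording and an extended visit field on the data form. There are two downsides. Complications that only needed a look leave the main event count. The supportive any-grade count may still differ by arm, because an in-person examination can detect minor findings more readily than video; this should be stated wherever that count is interpreted.
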